5.4.2. Examination of Subgroups and Covariates

The following is a list of subgroups that may be used in descriptive summaries and statistical analyses. Additional subgroups of clinical interest may also be considered.

- If the percentage of participants is small within a particular subgroup, then the subgroup categories may be combined prior to unblinding the trial.
- If the category cannot be refined further, then descriptive rather than statistical comparisons may be performed for the particular subgroup.
- For subgroup analysis, per European Medicines Agency Guideline on the investigation of subgroups in confirmatory clinical trials (EMA, 2019), factors defining a subgroup population may be put in three categories:
 1. Factors with strong reason to expect an inconsistent response to treatment across the different levels of the factor to an extent that would make an overall assessment uninterpretable. In this case separate trials should usually be planned.
 2. Factors with reason to consider it prognostic for outcome, or at least some biological plausibility or external evidence such that an inconsistent response might be observed. In this study, stratified randomization strata, key demographic and baseline characteristic factors, will fall into this category. For these factors, subgroup analyses will be performed but likely underpowered so that a formal proof of efficacy will not be available individually in all subgroups. If consistent findings across multiple comparisons were observed, then these analyses would still be suggestive of a generalizable finding from the overall population.
 3. Factors with good argumentation why consistency of response to treatment is plausible or for which there is absence of pharmacological rationale and absence of clinical evidence from which to determine the plausibility of consistent drug effects. The impact of factor(s) falling into this category will be explored.

Subgroup Category	Subgroup and Subgroup Levels
EMA Subgroup Category 2:	
Randomization Strata	
 • Baseline BMI: <30 kg/m², ≥30 kg/m² • Gender at Birth: female, male 
For analysis purposes, randomization strata will be derived using eCRF data (which may differ from the strata captured in RAMOS NG).
 
All statistical analyses will adjust for the above randomization strata, unless stated otherwise. Treatment-by-Strata interactions will be assessed as specified in the analysis sections.

Demographic and Baseline Characteristic Subgroups	
 • Age 
 - Descriptive summaries: < 35, 35 - < 50, ≥ 50 - Statistical analyses: < 50, ≥ 50 - FDAAA: ≤18, 19 - 64, ≥ 65 - EMA: 18 - 64, 65 - 84, ≥ 85 • Race

Subgroup Category	Subgroup and Subgroup Levels
EMA Subgroup Category 2:	
	
 - White; Non-White - Black/ African American; Non- Black/ African American - White, Black/African American, Other 
For statistical modelling of biomarkers, use White, Black/African American vs. Other. For other statistical modelling, use White vs Non-White.
 
 • Country (not used for statistical modelling) 
 - Canada - United Kingdom - Ireland - France - Germany - Spain - Italy - Switzerland - Austria - Netherlands - Belgium - Japan - Australia - United States • Region North America, Europe, Rest of World • Baseline CD4+ cell count (cells/mm³) 
 - <350, 350 to <500, ≥ 500 cells/mm³ • Derived Maintenance Baseline (Day 1) Centres for Disease Control and Prevention (CDC) category: 
 - Stage I, Stage II, Stage III • Baseline HIV-1 Subtype (if available at the time of the analysis) 
 - A, A1, AE, AG, B, C, Other • INI Regimen prior to BIK 
 - Raltegravir, Elvitegravir, Dolutegravir, none. • Duration of Prior ART (including BIK) use before study entry (<1 year, 1 - <2, 2 - <3 ,3-<4, >=4 years)

Subgroup Category	Subgroup and Subgroup Levels
EMA Subgroup Category 2:	
EMA Subgroup Category 3:	
ISR-related: Needle length	For the maximum toxicity grade of each preferred term of the common ISR (pain, induration, nodules and any other ISR with >=5% subjects in the Q2M treatment arm) during the maintenance phase: 
 • Needle Length for Last CAB Injection prior to and including the onset date of the earliest corresponding CAB ISR with maximum toxicity grade during the Maintenance Phase: (<1.5, 1.5 to <2, ≥2 inch); • Needle Length for Last RPV Injection prior to and including the onset date of the earliest corresponding RPV ISR with maximum toxicity grade during the Maintenance Phase: (<1.5, 1.5 to <2, ≥2 inch); 
Note: If there is no ISR of interest reported during maintenance phase for a subject, the needle length of last injection during maintenance phase will be used in the summary.

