- p. Only collect if the Withdrawal visit occurs at Month 6 or Month 12 (OLI and BIK); Month 5 or Month 11 (D2I).
- q. Whole blood/PBMC collection samples may be used for virologic analyses. PBMCs will be collected at baseline Day 1, Month 6, Month 12, or Withdrawal if prior to Month 12 (OLI and BIK). PBMCs will be collected at baseline Day 1, Month 5, Month 11, or Withdrawal if prior to Month 11 (D2I)
- r. Blood sample for insulin, HbA1c, and renal and bone biomarker assessments: **Renal:** CystatinC; Beta-2-Microglobulin; Retinol Binding Protein (RBP); **Bone:** bone specific alkaline phosphatase, procollagen type 1-N-propeptide, type 1 collagen cross-linked C-telopeptide, osteocalcin, 25 hydroxy-Vitamin D.
- s. Blood sample for **CCI**
- t. Informed consent for genetic research must be obtained before sample collection. Sample may be collected at any visit after signing informed consent, but preferably at the Day 1 visit.
- u. **One blood sample for CAB and RPV each to be collected at each PK timepoint.** At Month 1, for participants who elected to participate in the Oral Lead in, and Month 14 for participants who were randomized to BIK and switched to CAB LA + RPV LA in the Extension Phase and will participate in the Oral Lead in, Pre dose PK samples are to be collected: PRIOR to the final oral dose of CAB + RPV. **For pregnant participants** (on CAB+RPV arm): two blood samples for CAB and one RPV sample at each PK timepoint. Refer to protocol Section 10.6.6.3.
- v. Participants who elected to participate in the Oral Lead in before switching to CAB LA + RPV LA injections, will take final dose of oral lead-in regimen in the clinic at the Month 1/Month 14 visit and begin injections.
- w. If possible, injections should be spaced approximately 2 cm from one another and from the site of any previous injection and or any injection site reaction. Bring RPV LA to approximately room temperature prior to injecting. Time and location of injection (right or left) as well as needle length used will be collected in the eCRF. The first injection can be performed before central lab results become available and safety parameters are reviewed.
- x. Collect sample for these assessments ONLY if the Withdrawal visit occurs at Months 6 and 12 (OLI and BIK); Month 5 and 11 (D2I).
- y. Refer to Section 7.1 of the protocol for additional information on performing withdrawal assessments

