3.24.	Safety	207966/primary_15/T3.36 and T3.40	Event-level Summary of Drug-Related Injection Site Reaction Adverse Events by Investigational Product and Preferred Term (Maintenance Phase)	Include Overall ISR as a Preferred Term D2I, OLI and Q2M Investigational Product: "CAB LA" or "RPV LA", "CAB/RPV LA"	M6, M12

Safety: Tables					
No.	Population	GSK Standard/ Example Shell	Title	Programming Notes	Deliverable [Priority]
3.25.	Safety	207966/primary_15/T3.37 and T3.41	Summary of Overall and Common Subject-level Characteristics of Drug-Related Injection Site Reaction Adverse Events by Investigational Product and Preferred Term (Maintenance Phase)	Include Overall ISR as a Preferred Term D2I, OLI and Q2M Investigational Product: "CAB LA" or "RPV LA", "CAB/RPV LA"	M6, M12
3.26.	Safety	207966/primary_15/T3.35	Summary of Overall and Common Injection Site Reaction Adverse Events by Preferred Term, Visit, and Maximum Severity (Maintenance Phase)	Include Overall ISR as a Preferred Term D2I, OLI and Q2M	M6, M12
3.27.	Safety	207966/primary_15/T3.38 and T3.42	Summary of Overall and Common Drug-Related Injection Site Reaction Adverse Events by Investigational Product , Preferred Term, Visit and Maximum Severity (Maintenance Phase)	Include Overall ISR as a Preferred Term D2I, OLI and Q2M Investigational Product: "CAB LA" or "RPV LA", "CAB/RPV LA"	M6, M12
3.28.	Safety	207966/primary_15/T3.39 and T3.43	Summary of Maximum Drug-Related Injection Site Reaction Adverse Event Grade by Investigational Product , Preferred Term and Needle Length (Maintenance Phase) - Common ISRs	Do not include Overall ISR as a Preferred Term D2I, OLI and Q2M Investigational Product: "CAB LA" or "RPV LA"	M6, M12
Laboratory: Chemistry and Hematology					
3.29.	Safety	Shell SAF_T6	Summary of Chemistry Changes from Baseline by Visit	ICH E3	M6, M12, EOS
3.30.	Safety	Shell SAF_T7	By Phase Summary of Maximum Emergent Chemistry Toxicities	207966/primary_15/T3.48	M6, M12, EOS
3.31.	Safety	Shell SAF_T6	Summary of Hematology Changes from Baseline by Visit	ICH E3	M6, M12, EOS

Safety: Tables					
No.	Population	GSK Standard/ Example Shell	Title	Programming Notes	Deliverable [Priority]
3.32.	Safety	Shell SAF_T7	By Phase Summary of Maximum Emergent Hematology Toxicities	207966/primary_15/T3.50	M6, M12, EOS
Laboratory: Urinalysis					
3.33.	Safety	207966/primary_15/T3.39 and T3.52	Summary of Urinalysis Dipstick Results by Visit (Maintenance Phase)		M6, M12

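### Table 3.28 assigns needle length by outcome, which can create a spurious needle-length difference in ISR severity if needles drift over the study or are changed after reactions

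*SAP*

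**What the plan says.** SAP Section 5.4.2 lists needle length as an ISR-related subgroup factor with three classes (<1.5, 1.5 to <2, ≥2 inch). For participants with an ISR of a given preferred term, the class is the "Needle Length for Last CAB Injection prior to and including the onset date of the earliest corresponding CAB ISR with maximum toxicity grade", with a parallel rule for RPV. For a participant with no such ISR in the Maintenance Phase, "the needle length of last injection during maintenance phase will be used in the summary".

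The rule feeds Safety Table 3.28 in Section 16.15.7, which shows maximum drug-related ISR grade by product, "Preferred Term and Needle Length (Maintenance Phase) - Common ISRs". Note 21 to Table 3 in Section 8.1 sends this summary back to Section 5.4 for the needle derivation. Section 8.2.1 attributes reactions that occurred to a needle by side of injection. It gives no rule for participants without a reaction and also points back to Section 5.4.2.

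Needle length sits in EMA subgroup category 3, for which the SAP says: "The impact of factor(s) falling into this category will be explored". No test, model or decision rule is attached to the table.

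**The concern.** A participant with an ISR can be indexed at any injection, whereas one without who completes the Maintenance Phase is always indexed at the last. For someone who changes needle, the group therefore depends on whether, and when, a reaction occurred. If use shifts from one length to another, the earlier length keeps the early reactors while its reaction-free users are counted under the later length.

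Comparing ISR severity between needle lengths is the only purpose of Table 3.28. If the grouping rule can itself produce a difference, a reader cannot tell artefact from effect.

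**Working it through.** The SAP states no figure for this summary, so there is none to reproduce. The check asks what the rule yields when needle length has no effect.

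**1. When the rule does harm.** Suppose needle choice is unrelated to ISRs. Let p_k be the share of participants on the longer needle at injection k, and w_k the share of those with an ISR who are indexed at injection k. The rule then gives:

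- longer-needle share among participants with an ISR: Σ w_k p_k
- longer-needle share among participants without one: p at the last injection

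If p_k is the same at every injection, the two shares are equal and there is no artefact. If p_k rises, the first falls below the second and the shorter needle looks worse.

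**2. Hand illustration, one-directional switching (all inputs assumed).** 10% always use the longer needle; a share s switches from shorter to longer; the rest stay on the shorter. ISR risk is R for everyone. A fraction f = 0.6 of switchers' index ISRs precede the switch.

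- Shorter = [(0.9 − s)R + sRf] / [(0.9 − s) + sRf]
- Longer = [0.1R + sR(1 − f)] / [0.1 + sR(1 − f) + s(1 − R)]

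Results:

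- s = 0.1, R = 0.6: 0.516/0.836 = 61.7% v 0.084/0.164 = 51.2%
- s = 0.2, R = 0.6: 0.492/0.772 = 63.7% v 0.108/0.228 = 47.4%
- s = 0.1, R = 0.3: 0.258/0.818 = 31.5% v 0.042/0.182 = 23.1%

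With f = 0 both groups equal R, so the artefact also depends on ISR timing.

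**3. Simulation of the rule, true difference zero.** From the SAP: seven planned injections to Month 11/12 (Sections 16.3.2.1 and 16.3.2.2). Assumed: 1,000,000 participants; two needle classes; half start on each unless stated; outside the reaction-driven row, switch time uniform over injections 2 to 7; a quarter of ISRs grade 2. Per-injection ISR risk is either early-weighted (0.40, 0.25, 0.15, 0.10, 0.08, 0.06, 0.05) or constant at 0.15. The implied overall risks are 1 − 0.6×0.75×0.85×0.9×0.92×0.94×0.95 = 71.7% and 1 − 0.85^7 = 67.9%.

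Any ISR, shorter v longer (%), with the difference in points from unrounded values:

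| Assumed needle pattern | Early-weighted risk | Constant risk |
|---|---|---|
| No change | 71.8 v 71.8 (0.0) | 68.0 v 67.9 (+0.1) |
| Balanced switching, 20% | 71.7 v 71.8 (0.0) | 68.0 v 67.9 (+0.1) |
| Balanced switching, 40% | 71.6 v 71.6 (0.0) | 67.9 v 68.1 (−0.1) |
| 30% redraw needle, 20% on longer throughout | 71.7 v 71.7 (0.0) | not run |
| Drift to longer, 10% of shorter starters | 73.5 v 70.2 (+3.2) | 69.2 v 66.7 (+2.4) |
| Drift to longer, 20% | 75.3 v 68.8 (+6.5) | 70.7 v 65.8 (+4.9) |
| Drift to longer, 40% | 79.5 v 66.1 (+13.5) | 74.5 v 63.9 (+10.5) |
| 20% switch either way, 80% start shorter | 74.3 v 64.0 (+10.3) | not run |
| 30% of shorter starters with an ISR go longer after the first | 71.1 v 72.3 (−1.1) | 67.2 v 68.6 (−1.3) |

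In the reaction-driven row the grade 2 figures are 23.0% v 26.0% (early-weighted) and 22.0% v 24.9% (constant), so the sign is reversed.

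**4. Alternatives on the same data.** Classifying everyone by the needle at the first injection gave a difference within 0.2 points in every scenario. ISRs per injection, by needle used, gave 15.0% v 15.0% with constant risk. With early-weighted risk and 20% drift, the per-injection figures were still 16.4% v 15.0%, because shorter-needle injections fall earlier, when risk is higher. Hence the need to stratify by visit.

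**The case against.** A reader might infer that any change of needle biases the table, that the earlier-used length always collects the excess, or that a wrong needle recommendation will follow. The documents support none of these. Balanced or stationary switching unrelated to ISRs leaves essentially no difference, and with no switching there is none. Switching after a reaction reverses the sign. The SAP shows only that needle length is recorded with injections ("as well as needle length used will be collected in the eCRF"), not that anyone changes it, and it plans no recommendation on needle choice.

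It is also fair that the hand illustration is an adverse case: all switchers move one way, few start on the longer needle, and f is a single value. It uses two classes where the SAP has three, and an overall risk where the table is split by product and preferred term. For participants who do react, tying severity to the needle used just before is sensible. The table shell is not in the document, so its exact denominators cannot be seen.

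These points limit size and reach. They do not remove the defect: Section 5.4.2 expressly brings participants without an ISR into the summary under a different index injection, and nothing else in the SAP corrects it. Exploratory status does not make an outcome-dependent grouping neutral.

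**Conclusion.** The point stands in a limited form. The classification in Section 5.4.2 depends on the outcome and can produce a needle-length difference in Table 3.28 where none exists. That requires needle length to drift over the study or to be changed in response to reactions.

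Under assumed one-directional drift in 10% to 40% of shorter-needle starters the artefact is about 2 to 14 percentage points (2.4 to 13.5 in the simulation). Reaction-driven switching gave about 1 point for any ISR and about 3 points for grade 2, in the opposite direction. These sizes rest on assumed switch rates and ISR timing that the SAP does not give, so neither size nor sign can be stated for this trial. The reach is one descriptive safety table; no primary, key secondary or treatment-arm comparison uses it.

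**What to change.** Replace the subject-level derivation with an injection-level one. For each visit, for CAB and RPV separately, and by preferred term and grade, divide the ISRs attributed to an injection by all injections given with that needle length at that visit. If intervals are shown, allow for repeated injections within a participant. Stratifying by visit deals with drift. If needles were changed because of reactions, differences between participants in their tendency to react could still confound the comparison, and a footnote should say so; the simulation did not include such differences.

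If a subject-level table is kept, classify every participant at the same index injection regardless of outcome, for example the first. The small downside is that a later ISR may then be tabulated under a needle other than the one used just before it.

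The cost is re-specifying one table and its shell. No new data are needed: needle length is already captured, and Section 8.2.1 already assigns ISRs to injection visits for the by-visit summaries. Table 3.28 is scheduled for the Month 6 and Month 12 deliverables, so if those have been run, one supplementary table suffices.

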5.5. Multiple Comparisons and Multiplicity

There are no planned adjustments for multiple comparisons or multiplicity.

5.5.1. Primary Analysis

The primary comparison of interest is the comparison between CAB LA + RPV LA (Q2M) and BIK for the primary endpoint in the mITT-E population at Month 12 (OLI and BIK)/Month 11 (D2I). The primary comparison will be made at a one-sided 2.5% level of significance. Treatment with CAB LA + RPV LA (Q2M) will be declared non-inferior to BIK if the upper bound of a two-sided 95% confidence interval for the difference (Q2M – BIK) in proportion of participants with HIV-1 RNA ≥ 50 c/mL is below 4%.

If the primary analysis demonstrates non-inferiority, then a superiority hypothesis will be tested at the two-sided 5% level of significance. Superiority favoring CAB LA + RPV LA (Q2M) will be declared if the upper limit of the confidence interval is below 0% for the mITT-E population analysis. If superiority is declared, the p-value for superiority will also be calculated.

No multiple comparison adjustment is necessary for testing non-inferiority followed by superiority (conditional on achieving significance in the non-inferiority test) since testing follows a pre-specified sequence of hypothesis such that if the first hypothesis tested is not significant, all subsequent tests will not be performed. This fixed sequence procedure controls the type I error rate at the nominal level.

Subjects who became pregnant during the study will be allowed to continue CAB LA + RPV LA (Q2M) treatment, while those who became pregnant on BIK will be withdrawn. To minimize bias, a “while on-treatment” strategy will be implemented. Viral load data collected after confirmed pregnancy will not be evaluated for summary tables and statistical analysis in the primary analysis (see [Appendix 13: Data Handling for Pregnant Subjects](#)).

5.5.2. Other Comparisons of Interest

The following sensitivity analysis will also be performed for consistency with the results from the primary analysis:

- Same analysis as described above with the PP population
- Same analysis as described above with the ITT-E population
- Same analysis as described above with all data as observed (not applicable if no subject on the Q2M arm becomes pregnant)

5.5.3. Secondary Comparisons

If the primary comparison of interest (Section 5.5.1) using the mITT-E population demonstrates non-inferiority of CAB LA + RPV LA (Q2M) compared to BIK at the primary analysis timepoint, then the following key secondary comparisons using the mITT-E population will be tested:

- Treatment comparisons between the two arms (Q2M – BIK) with respect to the proportion of participants with HIV-1 RNA < 50 copies/mL at Months 12 (OLI and BIK)/Month 11 (D2I) (defined by the US FDA snapshot algorithm), including the two-sided 95% confidence interval. If the lower limit of the confidence interval for the difference in response rates (Q2M-BIK) lies **above -12%** then non-inferiority can be concluded.
- Sensitivity analysis as described in Section 5.5.2 in the PP population and with all data observed will also be performed, for secondary comparisons. Additional comparisons of clinical interest between two treatment arms may also be performed as supportive analyses.
- In addition to the primary and the key secondary comparisons, the comparisons between two treatment arms for HIVTSQs (Treatment Satisfaction Status Score), HIVTSQc (Treatment Satisfaction Change score), the statistical test on change in PIN acceptance score within the Q2M arm over time using a two-sided 5% level of significance will also be performed as supportive analyses.

5.6. Other Considerations for Data Analyses and Data Handling Conventions

Other considerations for data analyses and data handling conventions are outlined in the appendices:

Section	Component
16.3	Appendix 3: Assessment Windows
16.4	Appendix 4: Study Phases and Treatment State
16.5	Appendix 5: Data Display Standards & Handling Conventions
16.5	Appendix 6: Derived and Transformed Data
16.7	Appendix 7: Reporting Standards for Missing Data
16.8	Appendix 8: Values of Potential Clinical Importance
16.9	Appendix 9: Snapshot Algorithm Details
16.10	Appendix 10: Variables Defined for Time to Event Analysis
16.11	Appendix 11: Identification of Adverse Events of Special Interest (AESI)
16.12	Appendix 12: Identification of COVID-19 Adverse Events
16.13	Appendix 13: Data Handling for Pregnant Subjects

6. STUDY POPULATION ANALYSES

6.1. Overview of Planned Study Population Analyses

The study population analyses will be based on the Intent-to-Treat Exposed population, unless otherwise specified. Note in the Month 12 analysis, mITT-E will be used in summary tables.

Study population analyses including analyses of participant's disposition, protocol deviations, demographic and baseline characteristics, prior and concomitant medications, and exposure and treatment compliance will be based on GSK Core Data Standards.

[Table 1](#) provides an overview of the planned study population analyses, with full details of data displays presented in [Appendix 15: List of Data Displays](#)

Table 1 Overview of Planned Study Population Analyses

Display Type	Data Displays Generated	
	Table	Listing
Randomization		
Randomization ^[1]		Y ^[2]
Subject Disposition		
Study Populations ^[3]	Y	
Study Recruitment ^[3]	Y	
Reasons for Screening Failures ^[3]	Y	Y
Age categories	Y	
Subject Disposition	Y ^{[4][5]}	
Reasons for Withdrawal	Y ^{[4][5]}	Y
IP discontinuation	Y	Y
Important Protocol Deviations	Y	Y
Deviations leading to exclusion from PP	Y	Y
Inclusion and Exclusion Criteria Deviations	Y	Y
Demography and Baseline		
Demographics Characteristics ^[6]	Y	Y
Race & Racial Combinations ^[7]	Y	Y
Hepatitis Status at Entry	Y	
CDC Classification of HIV infection (2014) at Maintenance Baseline (Day 1)	Y	
Distribution of CD4+ Cell Counts at Screening and Maintenance Baseline (Day 1)	Y	
HIV Risk Factors	Y	
Medical Conditions, Concomitant Medications & Antiretroviral Therapy		
Medical Conditions (Current/Past) ^[8]	Y	
Medical Conditions: Sub-conditions (Current/Past) ^[9]	Y	
Concomitant Medications (non-ART)	Y ^[10]	
Prior Antiretroviral Therapy	Y	Y
Concomitant Antiretroviral Therapy during Maintenance Phase		Y
ART Medications Received during LTFU Phase		Y
Lipid Modifying Agents (Maintenance Baseline (Day 1) and During Maintenance Phase)	Y	
Substance use at Screening	Y	
Medical History of Seizure		Y
Other		
Study Treatment Accountability ^[11]		Y

NOTES:

- T = Tables, L = Listings, Y = Display Generated,
- 1. Based on Randomized population
- 2. One listing of participants randomized but not treated, and one listing of planned and actual treatment strata.
- 3. All Subjects screened population.
- 4. Participants who have not been recorded as either completing or withdrawing from the study will be categorized as "Ongoing at time of the analysis" for summary purposes.
- 5. Analysis of subject disposition may be performed for each study Phase separately if applicable, as well as for overall study conclusion.
- 6. Age and ethnicity collected at Screening; weight, height and BMI collected at Day 1,
- 7. The five high level FDA race categories and designated Asian subcategories will be summarised along with all combinations of high-level categories which exist in the data. The nine race categories collected will be summarised along with categories for mixed race. A by-subject listing of race will also be produced.
- 8. Medical conditions will be coded using the Medical Dictionary for Regulatory Activities (MedDRA).
- 9. Sub conditions include Cardiac, Gastrointestinal, Metabolism and Nutrition, Psychiatric, Renal and Urinary, and Nervous system Conditions.
- 10. Summarised by Ingredient combinations.
- 11. Dispensation information (dates and number of tablets dispensed and returned).

7. EFFICACY ANALYSES**7.1. Primary Efficacy Analyses****7.1.1. Endpoint / Variables**

The primary objective of the study is to demonstrate the non-inferior antiviral activity of CAB LA + RPV LA every two months (Q2M) compared to a BIK single tablet regimen administered once daily over 12 months in suppressed HIV-1 infected antiretroviral therapy (ART)-experienced participants. The primary endpoint is proportion of participants with plasma HIV-RNA greater than or equal to 50 copies/mL as per Food and Drug Administration (FDA) Snapshot algorithm at Month 12 (OLI and BIK)/Month 11 (D2I).

